1 PROTOCOL SUMMARY

1.1 SYNOPSIS

Title:	Pilot Study of Omega-3 Polyunsaturated Fatty Acid Treatment in Mild Acute TBI (OPTIMA-TBI pilot).
Study Description:	This is a double-blinded randomized control trials comparing the effect of omega-3 fatty acid versus placebo on blood biomarkers of brain injury, inflammation and neurogenesis.
Objectives:	
Primary Objective: Biomarker endpoints include: neuronal injury measured by Neurofilament light chain (NFL), Neurogranin (NRGN) and Intercellular adhesion molecule 5 [ICAM5]; inflammation measured by high sensitivity C-reactive protein (CRP), IL-6 and IL-10 and neurogenesis measured by brain derived neurotrophic factor (BDNF)
 
Secondary Objectives:
 
1. Delayed functional recovery defined as Glasgow Outcome Scale Extended (GOSE)<8 at 3 months2. Moderate/severe post-concussive symptoms at 3 months defined as having at least three symptoms in at least three following ICD-10 symptom categories obtained from the Rivermead Post-Concussion Questionnaire (RPQ): (1) headaches, dizziness, general malaise, excessive fatigue, or noise intolerance; (2) irritability, emotional lability, depression, or anxiety; (3) subjective complaints of concentration or memory difficulty; (4) insomnia; (5) reduced tolerance to alcohol; (6) preoccupation with these symptoms and fear of permanent brain damage.3. Cognitive impairment at 3 months is defined based on a battery of 13 neurocognitive tests. Subjects are deemed cognitively impaired if their scores on at least 2 neurocognitive tests are more than 2 standard deviations below their IQ T-Score ascertained by the Wechsler Test of Adult Reading (WTAR).4. Serious adverse events (SAEs): Life-threatening bleed including upper GI bleed, intracranial hemorrhage; hypotension; severe allergic reaction, blood glucose and LDL cholesterol levels
Endpoints:	
Primary Endpoint: Serum levels of neurofilament light chain, C-reactive protein, IL-6, IL-10, Brain derived neurotrophic factor over a 3-month period
 
Secondary Endpoints: Functional recovery (measured by Glasgow Coma Scale Extended), symptomatic recovery (measured by the Rivermead Post-concussive Symptoms Questionnaire) and cognitive impairment (measured by a cognitive battery) at 3 months post injury

Study Population:	
Individuals presenting to the emergency department (ED) within 7 days of injury, who meet the American Congress of Rehabilitation Medicine (ACRM)'s definition of having mild traumatic brain injury (mTBI) will be eligible. The ACRM defines mTBI as a traumatically-induced physiological disruption of brain function as a consequence of the head being struck, striking an object, or undergoing an acceleration/deceleration movement without direct external head trauma and resulting in at least one of the following: any period of loss of consciousness (LOC); any loss of memory for events immediately before or after the injury; any alteration in mental state at the time of the injury (eg, feeling dazed, disoriented, or confused); and focal neurological deficit(s) that may or may not be transient. Subjects will be excluded if they have any of the following findings:
 
 1. GCS<13 at any time during ED stay 2. Significant polytrauma including: bony fracture or solid organ injury 3. Study medication cannot be administered within 7 days of injury 4. Patient cannot be relied on to complete follow-up (i.e. no reliable telephone number, substance dependence, homeless) 5. Cannot communicate in English 6. Take an anticoagulant (coumadin or a novel oral anticoagulant) daily 7. Age less than 18 years or greater than 65 years 8. Patients already taking fish oil supplements daily 9. History of cognitive impairment 10. Allergic to fish/fish oil 11. Pregnant women (self-reported)
Phase:	II
Description of Sites/Facilities Enrolling Participants:	University of Michigan Emergency Department
Description of Study Intervention:	The intervention group will receive 6g/day of omega-3 fatty acids (fish oil) for 1 month followed by 1.2g/day for two additional months. The control group will receive placebo (olive oil) treatment for 3 months.
Study Duration:	1 year
Participant Duration:	3 months

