1.2 SCHEMA

1.3 SCHEDULE OF ACTIVITIES (SOA)

Activity	Enrollment	2 week visit	1 month visit	3 month visit
Screening	X			
Demographics	X			
Medical History	X			
Pre-hospital Events	X			
Informed consent	X			
Clinical data elements	X			
Rivermead Post-Concussion Questionnaire	X	X	X	X
Blood draw	X	X	X	X
Study medication	X	X	X	X
Glasgow Outcome Scale Extended		X	X	X
Montreal Cognitive Assessment			X	X
Brief Test of Attention (BTA)			X	X
Trail Making Test, Part A, Part B			X	X
Stroop Test			X	X
Controlled Oral Word Association Test (COWAT)			X	X
Wisconsin Card Sorting Test (WCST)			X	X
Hopkins Verbal Learning Test (HVLT)			X	X
Brief Visual Memory Test (BVMV)			X	X
Wechsler Test of Adult Reading (WTAR)			X	X
Patient Health Questionnaire 9 (PHQ9)			X	X
Generalized Anxiety Scale GAD 7			X	X
Davidson Trauma Scale to assess PTSD			X	X
Pittsburg Sleep Questionnaire			X	X
Satisfaction with life scale			X	X
Social Ties Check List			X	X
McGill pain scale			X	X

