4 STUDY DESIGN

4.1 OVERALL DESIGN

We hypothesize that treatment of traumatic brain injury patients with omega-3 fatty acids will result in a decrease in blood concentrations of biomarkers of neuronal injury and inflammation and an increase in the blood concentration of biomarkers of neurogenesis. This is a randomized, placebo-controlled, double-blinded pilot phase II clinical trial. Participants will be randomized either a single dose of 6g of DHA+EPA for 1 month followed by 1.2g/day of DHA+EPA for two additional months or to placebo treatment for 3 months. Blood samples will be drawn at enrollment, 2 weeks, 1 month and 3 months post-injury. Biomarkers of neuronal injury, inflammation, and neurogenesis will be measured in batches. Functional and symptomatic recovery will be assessed at 2 weeks, 1 month and 3 months. Additionally, cognitive impairment will be assessed at 3 months.

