6.3 MEASURES TO MINIMIZE BIAS: RANDOMIZATION AND BLINDING

A web-based central randomization system will be developed and utilized. Study team members will be blinded to study group allotment.

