9 STATISTICAL CONSIDERATIONS

9.1 STATISTICAL HYPOTHESES

- Primary Efficacy Endpoint(s):

Omega-3 fatty acid supplementation results in a decrease in the area under the concentration versus time curve for neurofilament light chain, CRP, IL-6 and IL-10 during the 3 months following TBI and an increase in the area under the concentration curve for brain derived neurotrophic factor.

- Secondary Efficacy Endpoint(s):

Omega-3 fatty acid supplementation improves functional outcome, post-concussive symptoms and cognitive decline post-TBI

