9.2 SAMPLE SIZE DETERMINATION

This is a pilot study of 50 patients.

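### No stated analysis uses the RPQ scheduled at enrollment; a baseline-adjusted 3-month RPQ score beside the yes/no symptom rate would add a useful planning estimate at no cost

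*Combined protocol and SAP*

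**What the plan says.** - **Definitions.** Section 1.1 (Synopsis, Secondary Objectives) defines function as "Delayed functional recovery defined as Glasgow Outcome Scale Extended (GOSE)<8 at 3 months" and symptoms as "Moderate/severe post-concussive symptoms at 3 months defined as having at least three symptoms in at least three following ICD-10 symptom categories". Both are yes/no states at one time point.
- **Endpoint rows.** The endpoint row of the Synopsis and the endpoint column of Section 3 name only the instruments. They fix no scale, summary or model.
- **Schedule.** Section 1.3 marks the "Rivermead Post-Concussion Questionnaire" at enrollment, 2 weeks, 1 month and 3 months. The "Glasgow Outcome Scale Extended" is marked at the three later visits only.
- **Text on timing.** Section 4.1 says "Functional and symptomatic recovery will be assessed at 2 weeks, 1 month and 3 months". Section 8.1 gives the same three times. Neither mentions an enrollment RPQ.
- **Hypothesis.** Section 9.1 states that treatment "improves functional outcome, post-concussive symptoms and cognitive decline post-TBI", without a test, scale or covariate.
- **Analysis.** Section 9.3 (General Approach) describes a GEE regression for biomarkers. It has no analysis of RPQ or GOSE.
- **Purpose.** Section 3 wants preliminary data on the treatment effect on these outcomes, to help design a multi-center trial.

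**The concern.** When the product of a pilot is a preliminary effect estimate, the width of the interval around it matters more than a p-value. A yes/no symptom status at about 25 per arm gives a wide interval, and it ignores how symptomatic each participant was before treatment. The schedule already provides that pre-treatment measurement: Section 6.1.2 starts treatment after enrollment. As written, the enrollment RPQ would be collected and then play no part in any pre-specified comparison. If a score analysis is chosen only after the data are seen, the choice of scale and covariate is open to the criticism that it was made post hoc.

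**Working it through.** **Inputs from the documents**

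- Total size: "This is a pilot study of 50 patients" (Section 9.2). It comes with no alpha, power, effect size or event rate, so there is no planned figure to reproduce.
- Allocation: "A web-based central randomization system will be developed and utilized" (Section 6.3). No ratio is stated.

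**Assumptions (not in the documents)**

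- 1:1 allocation, so n = 25 per arm, with complete follow-up.
- A roughly normal RPQ total at 3 months. Widths are in units of its within-arm SD.
- Correlation ρ between enrollment and 3-month RPQ of 0.2 to 0.7. The documents give no value.

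**Step 1. Interval for the unadjusted score difference**

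Half-width = t(0.975, 2n − 2) × √(2/n) = 2.011 × √(2/25) = 2.011 × 0.2828 = 0.57 SD.

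**Step 2. Interval for the baseline-adjusted difference**

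Half-width = t(0.975, 2n − 3) × √(2/n) × √(1 − ρ²), with t = 2.012 on 47 degrees of freedom. This ignores the small allowance for chance imbalance in the baseline score. The equivalent unadjusted size per arm is 25/(1 − ρ²).

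| ρ (assumed) | √(1 − ρ²) | Half-width (SD) | Equivalent n per arm |
|---|---|---|---|
| 0.2 | 0.980 | 0.56 | 26.0 |
| 0.3 | 0.954 | 0.54 | 27.5 |
| 0.5 | 0.866 | 0.49 | 33.3 |
| 0.7 | 0.714 | 0.41 | 49.0 |

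The factor √(1 − ρ²) cuts the width by about 2%, 5%, 13% and 29%. Adjustment is nearly neutral at the low end and worth having from about 0.5 upward.

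**Step 3. Interval for the binary endpoint, for context**

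Wald half-width for a risk difference with common rate p = 1.96 × √(2p(1 − p)/25). For p = 0.2, 0.3, 0.4 and 0.5 this gives ±22, ±25, ±27 and ±28 percentage points. The rates are assumed.

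**Step 4. What Steps 2 and 3 do and do not say together**

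Step 2 concerns a difference in mean score and Step 3 a difference in proportions. The adjustment leaves the Step 3 widths as they are. The gain is an additional estimate that uses the whole scale and the baseline.

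**The case against.** The strongest reply is that the plan does not commit to a yes/no analysis. The endpoint entries in the Synopsis and Section 3 name only the instruments, and no analysis of any clinical outcome is written. A reader might infer that the plan prescribes a dichotomised analysis and discards the score. The documents do not support that: they are silent, and the wider gap is the missing secondary analysis plan. What stands is that the only working definition of the symptom outcome is binary and that the enrollment RPQ is used nowhere.

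Three further inferences are tempting and should be resisted.

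- **That adjustment would sharpen the very estimate the next trial needs.** Section 3 speaks of delayed recovery and moderate/severe symptoms, which are event rates. An ANCOVA on the total estimates something else. It serves planning directly if the next trial uses a continuous RPQ endpoint, which the documents do not say.
- **That the loss can be stated as power of a cut normal score against the uncut score.** The symptom definition is a rule across ICD-10 categories, not a cut of the total. GOSE is ordinal and cut at its top category. The usual efficiency figures transfer to neither.
- **That the same gain applies to GOSE.** It has no enrollment value, and its ordinal gain is unquantified and may be small if most participants score 7 or 8.

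Two cautions on the baseline also stand. Enrollment can fall anywhere within 7 days of injury, so the enrollment RPQ is taken at varying acute stages and its correlation with 3 months may be low. Sections 4.1 and 8.1 also omit this assessment, so its collection rests on the schedule alone.

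**Conclusion.** The point holds for the RPQ, at modest severity. The plan schedules a pre-treatment symptom score, defines the symptom outcome only as a yes/no state at 3 months, and writes no analysis that uses the baseline. A baseline-adjusted score analysis would give a half-width of 0.41 to 0.56 SD against 0.57 SD unadjusted, over assumed correlations of 0.7 down to 0.2. These figures rest on 1:1 allocation, complete follow-up, a normal score and a correlation the documents do not give.

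The benefit is a second, more informative estimate for planning, with no change in the precision of the risk difference. This is a secondary endpoint of a 50-patient pilot with no claimed power, so the cost of leaving it is a less informative preliminary result, not a failed test.

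**What to change.** 1. In Section 9.3, add an ANCOVA of the 3-month RPQ total with treatment arm and enrollment RPQ as terms, reporting the adjusted mean difference with its 95% confidence interval. State how the total is scored, since the documents define no total, and that the enrollment RPQ is taken before the first dose.
2. Keep the yes/no symptom outcome. Report the rate in each arm and the risk difference with 95% confidence intervals, as the event rate for planning.
3. Reconcile Sections 4.1 and 8.1 with the Schedule of Activities on whether the RPQ is collected at enrollment.
4. Optionally, add a proportional-odds comparison of GOSE at 3 months, labelled supportive, beside the planned cut.

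The cost is a few sentences in the analysis section and one extra model, or two with the GOSE comparison. No new data or visits are needed if the schedule is followed.

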1.2 SCHEMA

1.3 SCHEDULE OF ACTIVITIES (SOA)

Activity	Enrollment	2 week visit	1 month visit	3 month visit
Screening	X			
Demographics	X			
Medical History	X			
Pre-hospital Events	X			
Informed consent	X			
Clinical data elements	X			
Rivermead Post-Concussion Questionnaire	X	X	X	X
Blood draw	X	X	X	X
Study medication	X	X	X	X
Glasgow Outcome Scale Extended		X	X	X
Montreal Cognitive Assessment			X	X
Brief Test of Attention (BTA)			X	X
Trail Making Test, Part A, Part B			X	X
Stroop Test			X	X
Controlled Oral Word Association Test (COWAT)			X	X
Wisconsin Card Sorting Test (WCST)			X	X
Hopkins Verbal Learning Test (HVLT)			X	X
Brief Visual Memory Test (BVMV)			X	X
Wechsler Test of Adult Reading (WTAR)			X	X
Patient Health Questionnaire 9 (PHQ9)			X	X
Generalized Anxiety Scale GAD 7			X	X
Davidson Trauma Scale to assess PTSD			X	X
Pittsburg Sleep Questionnaire			X	X
Satisfaction with life scale			X	X
Social Ties Check List			X	X
McGill pain scale			X	X

2 INTRODUCTION

2.1 STUDY RATIONALE

The objective of this study is to determine whether the treatment of traumatic brain injury patients with omega-3 fatty acids results in a decrease in blood biomarkers of neuronal injury and inflammation and an increase in biomarkers promoting neurogenesis.

2.2 BACKGROUND

Primary brain injury, the initial physical injury to brain tissue post-trauma, responds only to measures that prevent TBI from occurring in the first place. However, secondary brain injury, a complex cascade of events causing additional brain injury following primary brain injury, is more amenable to pharmacologic treatment. Neuroinflammation is one of the recognized mechanisms of secondary brain injury. In response to primary brain injury, activated microglia and injured neurons both release signaling proteins including cytokines and chemokines. Ω -3 and ω -6 fatty acids are major components of immune cells and neuronal cell membranes. They are also precursors to neuromodulatory lipids such as eicosanoids, endovanilloids and endocannabinoids that have antinociceptive and anxiolytic properties.

Docosahexaenoic acid (DHA) is one of the most abundant fatty acid components of brain cell membrane phospholipids.¹ In rodent model studies, dietary supplementation with omega-3 fatty acids (eicosapentaenoic acid [EPA] and docosahexaenoic acid [DHA]) decreased secondary axonal injury,^{2,3} attenuated endoplasmic reticulum stress response,⁴ decreased neuroinflammation post-TBI,⁵ and improved short and long-term neurologic outcomes.³ Additionally, DHA supplementation post-TBI enhances neurogenesis by counteracting reductions in neuroplasticity biomarkers such as brain-derived neurotrophic factor.^{6,7} Furthermore, DHA deficient rodents are more likely to have a greater amount of axonal injury and slower recovery neurologic recovery post-TBI.⁸ To our knowledge there are no human studies examining the effect of omega-3 fatty acid supplementation post-TBI on functional, symptomatic and neurologic outcomes. However, a study of collegiate football players who were randomized to 2, 4 or 6g/day of DHA or placebo for a total of 189 days (including 80 pre-season days). Irrespective of the dose of DHA supplementation, those receiving DHA had lower values of serum neurofilament light chain, a biomarker of axonal injury, than those receiving placebo.⁹

2.3 RISK/BENEFIT ASSESSMENT

2.3.1 KNOWN POTENTIAL RISKS

Gastrointestinal distress (nausea, vomiting, diarrhea), low risk of bleeding

2.3.2 KNOWN POTENTIAL BENEFITS

Improvement in functional, cognitive and symptomatic recovery from traumatic brain injury; cardiovascular benefits

2.3.3 ASSESSMENT OF POTENTIAL RISKS AND BENEFITS

Omega-3 fatty acids have an excellent safety profile. It is FDA approved for treating hypertriglyceridemia. The potential risks from taking omega-3 fatty acids are minimal. Gastrointestinal symptoms resolve upon stopping the medication. The risk of bleeding is minimal and at times disputed. There are currently no treatments for traumatic brain injury. Animal studies have demonstrated that omega-3 fatty acid supplementation may hasten recovery from TBI. Therefore the potential benefits from taking this medication outweigh the risks.

3 OBJECTIVES AND ENDPOINTS

OBJECTIVES	ENDPOINTS	JUSTIFICATION FOR ENDPOINTS
Primary		
To determine the effect of omega-3 polyunsaturated fatty acids (PUFA) treatment on blood biomarkers of neuronal injury and blood biomarkers of inflammation and a blood biomarker of neurogenesis	Neurofilament light chain [NFL], Neurogranin [NRGN] and Intercellular adhesion molecule 5 [ICAM5], high sensitivity C-reactive protein [CRP], IL-6, IL-10, and brain derived neurotrophic factor [BDNF]	If omega-3 fatty acid supplementation decreases the levels of biomarkers of neuronal injury and inflammation and increases the levels of biomarkers of neurogenesis, then there is a strong likelihood it will improve clinical outcome
Secondary		

 1. To demonstrate the feasibility of enrolling, treating and conducting follow-up assessments on mTBI patients presenting to the University of Michigan 2. To acquire preliminary data on the effect of omega-3 PUFA treatment on delayed functional recovery, moderate/severe post-concussive symptoms and cognitive impairment. 3. To acquire preliminary data on the types and incidence of serious adverse events (SAEs) in the Omega-3 PUFA treatment arm compared to the placebo arm 	
 1. Successful enrollment of 50 subjects within 1 year 2. Measurement of functional recovery using the Glasgow Outcome Scale Extended (GOSE), measurement of symptomatic recovery using the Rivermead Post-concussive symptoms questionnaire (RPQ) and cognitive impairment using a neurocognitive battery of tests 3. Measurement of the incidents of gastrointestinal distress and clinically significant bleeding 	These endpoints will help inform the design of a multi-center phase II trial

4 STUDY DESIGN

4.1 OVERALL DESIGN

We hypothesize that treatment of traumatic brain injury patients with omega-3 fatty acids will result in a decrease in blood concentrations of biomarkers of neuronal injury and inflammation and an increase in the blood concentration of biomarkers of neurogenesis. This is a randomized, placebo-controlled, double-blinded pilot phase II clinical trial. Participants will be randomized either a single dose of 6g of DHA+EPA for 1 month followed by 1.2g/day of DHA+EPA for two additional months or to placebo treatment for 3 months. Blood samples will be drawn at enrollment, 2 weeks, 1 month and 3 months post-injury. Biomarkers of neuronal injury, inflammation, and neurogenesis will be measured in batches. Functional and symptomatic recovery will be assessed at 2 weeks, 1 month and 3 months. Additionally, cognitive impairment will be assessed at 3 months.

4.2 SCIENTIFIC RATIONALE FOR STUDY DESIGN

There are limited data on treatment of TBI with omega-3 fatty acids. The performance of a randomized control trial will allow an unbiased determination of the efficacy of omega-3 fatty acids in treating TBI

4.3 JUSTIFICATION FOR DOSE

Some animal studies have used a dose of 40mg/kg. Human studies of high dose omega-3 fatty acids for preventing cardiovascular disease have used our study dose of 4g. The maximum tolerable dose of omega-3 fatty acids is 21g/day. Case reports of severe TBI treatment with omega-3 fatty acids have reported using up to 19g/day. In our population of mild TBI patients we have selected a dose of 6g/day which is about 2 times the dose used in animal studies but significantly below the maximum tolerable dose or the dose used in other TBI studies.

4.4 END OF STUDY DEFINITION

A participant is considered to have completed the study if he or she has completed all phases of the study including the last visit or the last scheduled procedure shown in the Schedule of Activities (SoA), Section 1.3. The end of the study is defined as completion of the last visit or procedure shown in the SoA in the trial globally.

5 STUDY POPULATION

5.1 INCLUSION CRITERIA

Individuals presenting to the emergency department (ED) within 7 days of injury, who meet the American Congress of Rehabilitation Medicine (ACRM)'s definition of having mild traumatic brain injury (mTBI) will be eligible. The ACRM defines mTBI as a traumatically-induced physiological disruption of brain function as a consequence of the head being struck, striking an object, or undergoing an acceleration/deceleration movement without direct external head trauma and resulting in at least one of the following: any period of loss of consciousness (LOC); any loss of memory for events immediately before or after the injury; any alteration in mental state at the time of the injury (eg, feeling dazed, disoriented, or confused); and focal neurological deficit(s) that may or may not be transient.

5.2 EXCLUSION CRITERIA

Subjects will be excluded if they have any of the following findings:

1. GCS<13 at any time during ED stay.
2. Significant polytrauma including: bony fracture or solid organ injury
3. Study medication cannot be administered within 7 days of injury
4. Patient cannot be relied on to complete follow-up (i.e. no reliable telephone number, substance dependence, homeless)
5. Cannot communicate in English
6. Take an anticoagulant (coumadin or a novel oral anticoagulant) daily
7. Age less than 18 years or greater than 65 years
8. Patients already taking fish oil supplements daily
9. History of cognitive impairment
10. Allergic to fish/fish oil
11. Pregnant women (self-reported)

